1. INTRODUCTION AND RATIONALE

Invasive aspergillosis (IA) is the leading cause of infection-related death in patients with acute leukemia and in hematopoietic stem cell transplant (HSCT) recipients. Various pathophysiological changes in severely ill patients, such as cancer patients, can affect the pharmacokinetics of antimicrobial agents. Adequate posaconazole drug exposure is associated with better treatment outcome. Until recently, posaconazole drug absorption was compromised by drug-drug interactions and insufficient food intake. This resulted in substantial intra- and interindividual patient variability in the pharmacokinetics of posaconazole [Dolton *et al* AAC 2014, Brüggemann *et al* CID 2009, Alffenaar *et al* CID 2009, Dolton *et al* AAC 2012, Vaes *et al* AAC 2012, Tonini *et al* AAC 2012]. The introduction of the new oral formulation and intravenous preparation improved drug exposure. [Maertens *et al* AAC 2014, Kraft *et al* AAC 2014].

For voriconazole it was recently shown by our group that metabolism of voriconazole was influenced by severe inflammation, measured by C-reactive protein value [van Wanrooy *et al* AAC 2014, Encalada Ventura *et al* AAC 2015; manuscript in preparation of study with clinical trials.gov identifier NCT02074462]. The underlying mechanism was cytokine induced down regulation of cytochrome P450 expression. The reduced metabolism resulted in voriconazole plasma concentrations exceeding the therapeutic window of voriconazole posing the patient at risk for toxicity. Subsequently, dosages were adjusted to remain the voriconazole plasma concentration within the therapeutic window. However, when the degree of inflammation decreased and thereby the metabolism of voriconazole increased, patients were at risk for subtherapeutic drug concentrations. Therefore, it was concluded that inflammation should be taken into account when therapeutic drug monitoring of voriconazole is performed.

As posaconazole is only metabolized in limited extend by cytochrome P450 enzymes it is likely that posaconazole is not influenced by inflammation. However, no published data is available to support the hypothesis that exposure of posaconazole is not influenced by inflammation. Data on stable posaconazole exposure during treatment will result in a clinical benefit over voriconazole.

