4. STUDY POPULATION

4.1 Population (base)

Patients that receive posaconazole for treatment or (secondary) prophylaxis of fungal infections

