10.2 Longitudinal data analysis

The longitudinal data of the posaconazole concentration will be analyzed with a linear mixed model. A log transformation will be performed if the data are not normally distributed. A random additive effect will be selected for patients to address different concentrations between patients. A first-order autoregressive correlation between posaconazole trough concentrations over time will also be selected to correct for differences in intervals between observations. To investigate the effect of inflammation on posaconazole concentration, the Wald type III test will be conducted after correcting for gender, age, posaconazole dose and route of administration, liver enzymes (ALP, ALAT, ASAT, γ -GT and total bilirubin) and the use of interacting co-medication. The analysis will be performed using SAS 9.3 (SAS Institute Inc., Cary, NC, USA). A p value < 0,05 is considered statistically significant.

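### Section 10.2 gives each patient a random intercept but all patients one CRP slope; if slopes differ, the standard error of the inflammation test is too small

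*Combined protocol and SAP*

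**What the plan says.** Section 10.2 of the combined protocol and SAP states that "The longitudinal data of the posaconazole concentration will be analyzed with a linear mixed model". On patient-level random terms it says only that "A random additive effect will be selected for patients", and the purpose it gives is that concentrations differ from one patient to another. For the residuals, "A first-order autoregressive correlation between posaconazole trough concentrations over time will also be selected". Then "the Wald type III test will be conducted after correcting for gender, age, posaconazole dose and route of administration", with five liver tests and interacting co-medication as further covariates. The decision rule is "A p value < 0,05 is considered statistically significant".

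Section 4.4 plans 30 patients and expects three to four data points per treatment week; the number of weeks is not given. Section 8.3 names CRP as the inflammatory marker and rules out IL-6, IL-8 and procalcitonin.

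Neither section 10.2 nor any other section mentions a random slope, a robust standard error, a denominator degrees-of-freedom method, or a sensitivity analysis for patients who respond differently to inflammation.

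**The concern.** A random intercept absorbs differences in level. It says nothing about differences in slope, and autoregressive residuals do not supply that either. Repeated samples from one patient inform that patient's own slope. If slopes vary, the precision of the average slope is limited by the number of patients, and further samples per patient cannot remove that limit. The planned standard error keeps falling as samples accumulate.

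Varying slopes are plausible here, though the support is indirect. On earlier absorption problems, section 1 says "This resulted in substantial intra- and interindividual patient variability in the pharmacokinetics of posaconazole". Section 6.1 lists tablet, infusion and oral suspension together. The population in section 4.1 is "Patients that receive posaconazole for treatment or (secondary) prophylaxis of fungal infections". Section 5 allows dose changes guided by measured levels. Route and co-medication enter the model as covariates, with no interaction with CRP named, so they shift levels and not slopes.

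The Wald test is the only test specified for the effect of inflammation. The Summary and section 1 expect no influence, and sections 3 and 5 aim at a dosing algorithm. A standard error that is too small would raise the false-positive rate for the average effect, and would also make a null result look more precise than it is.

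**Working it through.** The plan has no figure to reproduce: section 4.4 gives 30 patients without an effect size, SD or power.

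**Inputs from the documents.** 30 patients and 3-4 samples per week (4.4, 8.3); random intercept, AR(1), Wald test and a 0.05 threshold (10.2; two-sided assumed).

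**Assumed inputs.** m = 7, 14 or 28 equally spaced samples per patient (about 2, 4 and 8 weeks); log concentration with intercept SD 0.4, residual SD 0.3 and residual AR(1) 0.4; standardised CRP with AR(1) 0.7; true mean slope 0; between-patient slope SD τ from 0 to 0.20. No covariate other than CRP.

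**Expected size.** If v is the variance of the estimated mean slope when all slopes are equal, then approximately

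Var(estimated mean slope) = v + τ²/30.

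For τ = 0.10, τ²/30 = 0.000333, so the SD cannot fall below about 0.10/√30 = 0.0183. Taking v from the τ = 0 rows of the table:
- m = 7: √(0.0286² + 0.000333) = 0.034 (simulated 0.0362)
- m = 14: √(0.0183² + 0.000333) = 0.026 (simulated 0.0259)
- m = 28: √(0.0123² + 0.000333) = 0.022 (simulated 0.0219)

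**Simulation.** REML fits, 300 replicates per row. The last two columns use t with 29 df.

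| τ | m | True SD of estimate | Mean SE, planned model | Ratio | Type I error, planned | Type I error, clustered SE | Type I error, random slope |
|---|---|---|---|---|---|---|---|
| 0 | 7 | 0.0286 | 0.0287 | 1.00 | 5.3% | 4.7% | 5.0% |
| 0 | 14 | 0.0183 | 0.0195 | 1.06 | 4.0% | 4.0% | 2.7% |
| 0 | 28 | 0.0123 | 0.0129 | 1.05 | 4.0% | 5.0% | 2.7% |
| 0.05 | 7 | 0.0308 | 0.0289 | 0.94 | 7.3% | 6.0% | 5.0% |
| 0.05 | 14 | 0.0205 | 0.0196 | 0.96 | 7.3% | 4.7% | 5.0% |
| 0.05 | 28 | 0.0155 | 0.0131 | 0.85 | 9.3% | 5.3% | 5.0% |
| 0.10 | 7 | 0.0362 | 0.0295 | 0.81 | 10.0% | 6.7% | 6.0% |
| 0.10 | 14 | 0.0259 | 0.0201 | 0.77 | 12.7% | 4.7% | 5.0% |
| 0.10 | 28 | 0.0219 | 0.0136 | 0.62 | 20.7% | 5.3% | 5.3% |
| 0.20 | 7 | 0.0525 | 0.0318 | 0.61 | 21.3% | 7.3% | 7.0% |
| 0.20 | 14 | 0.0410 | 0.0217 | 0.53 | 33.7% | 3.7% | 3.7% |
| 0.20 | 28 | 0.0376 | 0.0150 | 0.40 | 41.3% | 4.3% | 4.3% |

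Monte Carlo error is about ±2.5 percentage points at a rate of 5%, and up to about ±5.5 at the highest rates. At τ = 0.05 with 7 or 14 samples, 7.3% cannot be told apart from 5%.

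**Separate runs, planned model, 30 patients.**
- 600 replicates per setting: 8% (m = 7) and 15% (m = 14) at slope SD 0.10, against 4-5% with a random slope; 5-8% at 0.05.
- 1,000 replicates: 11.5% (m = 7) and 16.9% (m = 14) at slope SD 0.10.
- Ten covariates added, m = 7: planned model 6-12%, random slope 5-6%, uncorrected clustered SE on 29 df 7-9%.
- Ten covariates added, 500 replicates, slope SD 0.05: planned model 5.0% (m = 7) and 6.4% (m = 14), uncorrected clustered SE 6.0% and 6.8%.

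**What a slope SD means.** In the table τ is per SD of CRP. At 0.05, 95% of patients lie within exp(±1.96 × 0.05), about -9% to +10% in concentration per SD of CRP; at 0.10, about -18% to +22%. If the slope is instead taken per unit of ln CRP, 0.05 gives exp(±1.96 × 0.05 × ln 10), about -20% to +25% per tenfold CRP, and 0.10 gives about -36% to +57%.

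**The case against.** The strongest reply is that the documents do not show that slopes differ. The variability described in section 1 is pharmacokinetic variability in general, put down to absorption problems that newer preparations have eased. Differences in level are what the random intercept is for, and mixing treatment with prophylaxis does not by itself imply different slopes. This stands: heterogeneity is plausible but not documented.

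Second, under the protocol's own expectation of no influence, every slope is zero and the planned test has the right size (4.0-5.3% in the table). Inflation needs patients who do respond, in directions that average to zero, and a rejection then is not plainly a wrong answer about influence. This also stands, but the study is meant to examine that expectation, and an average slope with an understated error is a poor basis for a dosing algorithm.

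Third, with ten covariates and slope SD 0.05, one set of runs showed no visible gain from clustered standard errors. That holds at the small SD. Where the planned model drifted to 12% with covariates, the random slope held 5-6%.

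Fourth, the plan does not fix the scale on which CRP enters, so a slope for log CRP cannot be prescribed. This is correct, and the fix allows for it.

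Two stronger readings are tempting. A reader might infer that the model counts all samples as nearly independent, so that the real sample size is 30. The autoregressive term contradicts the first part, and the second is only the limit under large heterogeneity: at τ = 0.05 with 7 or 14 samples the SE ratio is 0.94-0.96. A reader might also infer that a primary test or its confidence interval is invalid. The plan labels no test primary, words its primary objective as exploratory, and promises no confidence interval.

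**Conclusion.** The point holds conditionally. As written, the inflammation test assumes one CRP slope for all patients, and its standard error is too small if slopes differ. With 30 patients, type I error is about nominal with equal slopes, about 5-9% at slope SD 0.05 and about 8-21% at 0.10, growing with samples per patient. Section 8.3 sets no limit on the sampling period, so the longer follow-up is possible.

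The slope SD, variance components, CRP process and number of samples are all assumptions, and the main table has no covariates besides CRP. The documents do not support any single figure as the study's actual error rate. This is a cheap improvement to the analysis plan; nothing here shows that the planned result will be wrong.

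**What to change.** In section 10.2, add to the random intercept a patient-level random slope for CRP, on the same scale as the fixed CRP effect, with intercept-slope covariance. State a small-sample degrees-of-freedom method such as Kenward-Roger for the test.

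Pre-specify the fallback: if the slope variance does not converge or lies at the boundary, keep the random intercept and use patient-clustered standard errors with a small-sample bias correction, with degrees of freedom based on the number of patients analysed. The correction matters, because the uncorrected version on 29 df ran at 7-9% with 7 samples and ten covariates. The table used t with 29 df for both alternatives and did not test Kenward-Roger or a bias-corrected clustered SE.

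The text cost is two or three sentences. With equal slopes, standard errors widen by about 2-7% across the simulations; in the table's runs the mean SE went from 0.0287 to 0.0294, 0.0195 to 0.0198 and 0.0129 to 0.0134 for 7, 14 and 28 samples. When slopes differ they widen more, as they should: at τ = 0.10, from 0.0295 to 0.0346 (17%), 0.0201 to 0.0268 (33%) and 0.0136 to 0.0224 (65%). The random slope also estimates how much patients differ, which a dosing algorithm would need.

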4.4 Sample size calculation

To be able to develop and validate a model based on inflammatory markers and posaconazole multiple data points are mandatory. We estimate that it is feasible to collect 3-4 data points per treatment week.

Taken into account the non-invasive nature of this study, the routine sampling of critically ill patients we plan to recruit 30 patients for this study.

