5. TREATMENT OF SUBJECTS

Subjects receive posaconazole as standard treatment or (secondary) prophylaxis for fungal infection. As the treatment with posaconazole and TDM are part of routine care they are neither initiated nor altered for study purposes (no intervention). Therefore this study is not being subjected to Medical Research Involving Human Subjects Act. Only data of standard care and TDM will be collected to develop the dosing algorithm for posaconazole during severe inflammation.

Attending physicians are allowed to request drug concentration measurement for patient care. If the posaconazole concentration is low the attending hospital pharmacist will provide the attending physician with a dosage advice. Dosages will be increased if levels are too low or decreased if levels are too high. The increase or decrease of the dosage will be based on the measured concentration, initial dosage and patient characteristics. Follow up will be performed to assure that the level reaches and remains in the therapeutic window.

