8.3 Study procedures

-Patients starting on posaconazole treatment will be evaluated for inclusion.

-After informed consent is obtained medical data will be collected from the medical chart and plasma samples from routine analysis will be obtained.

-Samples for posaconazole and inflammatory analysis will be collected 3-4 times weekly during treatment. Inflammatory markers like CRP will be determined by the department of Clinical Chemistry of the UMCG. Other inflammatory markers of IL-6, IL-8 and procalcitonin will not be determined, since these markers are not routinely measured. Posaconazole plasma concentrations (trough levels) will be measured with a validated and externally tested LC-MS/MS method of analysis [Alffenaar *et al* J Chrom B 2009].

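### Section 10.2 relies on a first-order autoregressive correlation to handle unequal sampling intervals but does not tie it to elapsed days

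*Combined protocol and SAP*

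**What the plan says.** Section 10.2 specifies a linear mixed model with two sources of within-patient dependence. The first is a patient intercept: "A random additive effect will be selected for patients to address different concentrations between patients". The second is serial correlation: "A first-order autoregressive correlation between posaconazole trough concentrations over time will also be selected to correct for differences in intervals between observations". The effect of inflammation is then tested in this model: "the Wald type III test will be conducted after correcting for gender, age, posaconazole dose and route of administration", followed by liver enzymes and interacting co-medication, at the 0.05 level in SAS 9.3. Neither this section nor any other names a time variable, a repeated effect or a SAS covariance type.

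On sampling, section 8.3 says "Samples for posaconazole and inflammatory analysis will be collected 3-4 times weekly during treatment", and also that "plasma samples from routine analysis will be obtained". It fixes no days. Section 5 adds "Attending physicians are allowed to request drug concentration measurement for patient care". Section 4.4 plans 30 patients and gives no effect size, variance or power.

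**The concern.** A first-order autoregressive structure needs a time index, and two are in ordinary use. On elapsed days, correlation falls with the actual gap, which is what section 10.2 wants. On observation order, two successive samples get the same correlation whether they are one day or five days apart, so equal spacing is assumed and nothing is corrected. The plan states an aim that only one of the two meets, and leaves the choice to whoever writes the code.

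The choice matters only if gaps vary. Routine sampling on unfixed days, plus levels requested for care, makes that likely.

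At stake is the Wald test of inflammation. Under the conditions examined below, an order-based fit to unevenly spaced data understates the standard error of the CRP slope and estimates the slope less precisely than the data allow. The introduction expects that "it is likely that posaconazole is not influenced by inflammation". A non-significant p value is weak support for that expectation; a valid and reasonably tight estimate of the slope would support it better. Both costs therefore count, although the plan itself mentions a p value and no interval.

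**Working it through.** **Inputs from the documents:** 30 patients (4.4), 3–4 samples a week (4.4, 8.3), random patient intercept and AR(1) (10.2), 5% level (10.2). There is no stated figure to reproduce.

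**Assumed, not in the documents:** four weeks of follow-up; true CRP effect zero; between-patient variance 0.15 and within-patient variance 0.10; log-CRP variance 1 with 1-day autocorrelation 0.85; true posaconazole correlation decaying by day.

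**Step 1: what each index implies.** By day, the correlation at a gap of g days is ρ^g. For ρ = 0.7 this is 0.70, 0.49, 0.34 and 0.08 at 1, 2, 3 and 7 days; for ρ = 0.9 it is 0.90, 0.81, 0.73 and 0.48. By order, every adjacent pair shares one value. In simulated 3–4-per-week data (2–4 weeks) that value averaged 0.53 and 0.82 respectively, and 0.42 and 0.76 when 35% of samples were missed.

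**Step 2: large-sample effect on the CRP slope, no measurement noise.** Let S be the true covariance, W the inverse of the best-fitting working covariance, and C the CRP covariance, summed over patient schedules.
- Model SE / true SE: r = √[Σtr(WC) / Σtr(WSWC)]
- Test size: 2[1 − Φ(1.96 r)]
- Variance ratio: slope variance under the order-based fit divided by that under the true covariance

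Example: r = 0.906 gives 1.96 × 0.906 = 1.776, so size = 7.6%.

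| Schedule | 1-day correlation | r | Size | Variance ratio |
|---|---|---|---|---|
| 3–4 random days | 0.50 / 0.70 / 0.85 | 0.959 / 0.930 / 0.906 | 6.0 / 6.8 / 7.6% | 1.062 / 1.131 / 1.217 |
| 3–4 random weekdays | 0.50 / 0.70 / 0.85 | 0.949 / 0.916 / 0.889 | 6.3 / 7.3 / 8.1% | 1.075 / 1.161 / 1.265 |
| Mon/Wed/Fri | 0.50 / 0.70 / 0.85 | 0.995 / 0.991 / 0.988 | 5.1–5.3% | 1.006 / 1.015 / 1.025 |
| Every second day | any | 1.000 | 5.0% | 1.000 |

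In the first two rows, 30 patients give the precision of about 30/1.062 = 28.2 down to 30/1.265 = 23.7 patients under the day-based model. For random days at 0.85, r barely moves with 2 or 8 weeks of follow-up (0.910, 0.904) or with CRP autocorrelation 0.70 or 0.95 (0.920, 0.906).

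**Step 3: measurement noise.** Let 40% of the within-patient variance be noise, with random days and correlation 0.85. Then r = 0.948 by order (1.96 × 0.948 = 1.858, size 6.3%), 0.954 by day (1.870, size 6.2%) and 1.000 by day with a measurement-error term (5.0%). Over correlations 0.50–0.85, noise brings the order-based size to about 5.7–6.5%.

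**Step 4: REML simulation at the planned sample size.** 30 patients, about 420 samples, ten null covariates standing for the adjustment set in 10.2, and 4,000 runs per row (Monte Carlo ± 0.7–0.8 points).

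| Scenario | Order | Day | Day + measurement error |
|---|---|---|---|
| Random days, 0.85, no noise | 8.0% | 5.0% | 5.2% |
| Random days, 0.85, 40% noise | 6.3% | 6.4% | 5.0% |
| Weekdays, 0.85, no noise | 7.9% | 5.2% | 5.3% |
| Random days, 0.50, no noise | 6.5% | 5.5% | 5.5% |

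**Step 5: a smaller simulation with other assumptions.** Correlation 0.7 or 0.9, 2–4 weeks, 250 runs per scenario, Monte Carlo standard error about 1.4 points. On a regular schedule with gaps of 1–3 days, size by order against day was 5.6 vs 6.0% and 7.2 vs 6.8%; the variance ratio was (0.0258/0.0259)² = 0.99 and (0.0183/0.0171)² = 1.15. With 35% of samples missed, size was 5.6 vs 3.2% and 6.8 vs 2.4%; the variance ratio was (0.0336/0.0306)² = 1.21 and (0.0227/0.0206)² = 1.21. This supports the precision loss when gaps are uneven. It has too few runs to confirm or exclude a size of 6–8%.

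**The case against.** The strongest reply is that the sentence settles its own meaning. A correlation over time, chosen because intervals differ, makes sense only if time is elapsed time. A natural coding would also deliver it: with treatment day as the repeated variable and its levels pooled over patients, random-day sampling left no day empty in 2,000 of 2,000 simulated studies, so that coding is day-indexed. This largely stands. A reader might infer that the plan assumes equal spacing, or that its test will be wrong; the documents do not support that, because they simply do not state the index. What remains is that the words also permit an order-based fit, and nothing in the plan rules it out.

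A reader might also infer that 3–4 samples a week must be unevenly spaced. That does not follow: strict every-second-day sampling gives four samples one week and three the next, with equal gaps. Nor is bias in the CRP slope implied. If the mean model is right and samples are missing completely at random, the slope is unbiased under either index.

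Further, every correlation, variance and follow-up length above is assumed, the primary objective is exploratory, and the largest figures come from the noise-free, irregular schedules. All true, and these points limit the severity.

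Last, the measurement-error term goes beyond the ambiguity itself. It does, but Step 3 shows why it belongs in the same sentence: with substantial noise, naming the day index alone would leave the test at about 6%.

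**Conclusion.** The point holds as a modest, conditional one. Section 10.2 gives the autoregressive correlation a task that it performs on a day scale and not by observation order, and does not say which will be used. The stated purpose points to the day reading.

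If the order-based version were used on unevenly spaced samples, the no-noise calculations at 1-day correlation 0.50–0.85 give a standard error about 4–11% too small, a test size of about 6–8%, and a slope variance about 6–27% larger. The harm is close to nil for regular sampling and smaller with noise. These figures rest on the assumed values listed in the working. Dose changes driven by measured levels, which are part of routine care here, were not simulated. The change is worth making because it costs little and secures what the plan already intends.

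**What to change.** In section 10.2, replace the sentence on autoregressive correlation with:

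> Residual correlation within a patient will be modelled as a function of elapsed days between samples (SAS TYPE=SP(POW) on sampling day), alongside the random patient intercept and a measurement-error variance (LOCAL option); if that variance is estimated at zero or the model does not converge, the model without it will be reported.

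The cost is one sentence and one or two lines of code, and the date of every sample must be recorded. The measurement-error variance may be weakly estimated with 30 patients: with no true noise it came out near zero in 54–68% of simulated studies, without harm to test size. This is why the fallback is defined in advance. Robust standard errors are optional and not part of the fix; with 30 patients their test size was 5.7–6.9%, and they do not recover lost precision.

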Rationale: Posaconazole is indicated for prophylaxis of invasive aspergillosis and can also be used as treatment of several fungal infections. Therapeutic Drug Monitoring (TDM) of posaconazole can be performed to maintain efficacy, since exposure-respons relationships are described for posaconazole (ref Dolton AAC 2012: mail [name]). Recently was shown that the plasma concentration of another antifungal agent, voriconazole, is influenced by inflammation, measured by C-reactive protein value [van Wanrooy et al AAC 2014, Encalada Ventura et al AAC 2015; manuscript in preparation of study with clinical trials gov identifier NCT02074462]. During severe inflammation the metabolism of voriconazole is reduced via downregulation of cytochrome P450 enzymes, which results in high voriconazole plasma concentrations. Subsequently, dosages can be adjusted to avoid toxicity. However, if the degree of inflammation decreases again, the metabolism of the drug increases with as a result possible subtherapeutic drug concentrations. As posaconazole is only metabolized in limited extend by cytochrome P450 enzymes it is likely that posaconazole is not influenced by inflammation. However, no published data is available to support the hypothesis that exposure of posaconazole is not influenced by inflammation. Data on stable posaconazole exposure during treatment will result in a clinical benefit over voriconazole.

Objective: The objective of this study proposal is to determine if posaconazole drug exposure is influenced during different stages of inflammation.

Study design: A prospective observational study will be performed at the University Medical Center Groningen, the Netherlands to determine if posaconazole drug exposure is influenced by inflammation.

Study population: patients receiving posaconazole for treatment or (secondary) prophylaxis of fungal infections

Intervention (if applicable): none

Main study parameters/endpoints: Main study parameter is the posaconazole drug exposure during different stages of inflammation. Subsequently, a multiple linear regression model that describes the contribution of inflammation on posaconazole levels will be developed. At last, the relation between the change in CRP and change in drug plasma concentration from this study will be compared with the results of our earlier prospective voriconazole study [NCT02074462] based on matched patients.

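### A single CRP slope for treated and prophylaxis patients, with no term for indication, cannot separate inflammation acting on the posaconazole level from low levels contributing to a higher CRP

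*Combined protocol and SAP*

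**What the plan says.** Section 10.2 sets out the model: "The longitudinal data of the posaconazole concentration will be analyzed with a linear mixed model". It has a patient intercept ("A random additive effect will be selected for patients to address different concentrations between patients") and serial correlation ("A first-order autoregressive correlation between posaconazole trough concentrations over time will also be selected"). The test of interest is described as follows: "To investigate the effect of inflammation on posaconazole concentration, the Wald type III test will be conducted". The adjustment set listed there is sex, age, dose, route, five liver tests and interacting co-medication. The trough is the outcome and inflammation is a predictor. Indication appears neither as a covariate nor in an interaction with CRP, and no lag or analysis of the reverse direction is given.

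Section 4.1 defines the population: "Patients that receive posaconazole for treatment or (secondary) prophylaxis of fungal infections".

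On exposure and outcome, section 1 says "Adequate posaconazole drug exposure is associated with better treatment outcome", and the Summary (Rationale) supports drug monitoring "since exposure-respons relationships are described for posaconazole". Neither gives a size or mentions CRP in this connection. Both places expect that inflammation does not influence posaconazole.

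Sections 2 and 8.1.1 make the primary aim an exploration of exposure across stages of inflammation. The regression model is a secondary aim. Section 10.2 nevertheless holds the only significance test of inflammation in the plan.

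**The concern.** The plan reads the CRP coefficient as an effect in one direction, from inflammation to drug level. In a patient with an active fungal infection the arrow may also run the other way: a low level, poorer control of the infection, a higher CRP. That path produces a negative association between CRP and trough, opposite in sign to the increase expected if inflammation slows metabolism. In prophylaxis patients there is normally no fungal infection for the drug to control, so the path should be largely absent.

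Dose, route and liver tests do not block the path, and without an indication term the reader cannot see whether the two groups differ. If inflammation truly raises levels, the slope could be partly masked and the result would look closer to the expected absence of influence. If there is no true effect, the slope could show a false decrease.

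**Working it through.** **Inputs from the documents.** 30 patients (section 4.4); 3 to 4 samples per week (sections 4.4 and 8.3); random patient intercept plus AR(1), p < 0.05 (section 10.2). The sample size rests on feasibility, with no effect size, SD or power, so there is no figure of the plan to reproduce.

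**Inputs assumed.** Strength of feedback, share of patients treated, follow-up length, variances, autocorrelations, two-sided testing, and a true slope of +0.10 or 0 in ln trough per SD of CRP.

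**Step 1: sign.** Ignoring time, write trough y = βx + e and CRP x = -γy + u, with γ > 0 for the reverse path and u independent of e. Solving gives x = (u - γe)/(1 + βγ), so Cov(x, e) = -γ·Var(e)/(1 + βγ). For β ≥ 0 this is negative, and a regression of y on x estimates β + Cov(x, e)/Var(x), which is below β. The repeated-measures model can absorb some or all of this, so the size needs simulation.

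**Step 2: size.** All rows use 30 patients, half treated, feedback in treated patients only, and a random intercept plus AR(1) fit. Feedback is -1 ln CRP per ln unit of exposure, or, in the 14-sample rows, a long-run fall of 1 SD of CRP per ln unit.

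| Set-up | Pooled slope, true 0.10 | Treated / prophylaxis slope | Pooled slope, true 0 (rejections) |
|---|---|---|---|
| Previous 7-day mean of daily levels; 3 weeks; patient SD 0.4, AR SD 0.35; daily autocorrelation 0.8 | 0.072 | 0.045 / 0.104 | -0.033 (26%) |
| Same, recorded troughs only | 0.075 | 0.058 / 0.094 | not run |
| Previous 7-day mean; same SDs; 12 samples in 3 weeks; CRP autocorrelation 0.8, trough 0.5 or 0.8 per day | 0.091 to 0.094 | not reported | -0.002 to -0.006 (8 to 11%) |
| 14 samples; SDs 0.5 and 0.3; AR 0.5; CRP autocorrelation 0.7; exposure at the CRP sample that earlier troughs miss | 0.080 | 0.062 / 0.099 | -0.017 (13%) |
| Same, recorded earlier troughs only | 0.102 | 0.103 / 0.101 | +0.003 (5%) |

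A further run at feedback -1 gave pooled slopes of 0.090 to 0.093, and 7 to 9% rejections with no true effect. Each tabulated setting had 100 to 150 runs.

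**Step 3: what pooling does.** In the fourth set-up the pooled slope is close to the average of the group slopes:

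- feedback 0.5: (0.101 + 0.081)/2 = 0.091, simulated 0.091
- feedback 1: (0.099 + 0.062)/2 = 0.081, simulated 0.080
- feedback 2: (0.100 + 0.031)/2 = 0.066, simulated 0.064

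With every patient treated, the slopes are 0.084, 0.065 and 0.030. Mixing in prophylaxis patients therefore roughly halves the bias: at feedback 2 it is 0.10 - 0.064 = 0.036, against 0.10 - 0.030 = 0.070.

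**Step 4: precision of group slopes.** Simulated standard errors, prophylaxis group against pooled: 0.047/0.033 = 1.42, 0.040/0.028 = 1.43 and 0.030/0.021 = 1.43. This is about √2, as expected when each group holds half the patients.

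**The case against.** The best defence is that a correctly specified random-intercept plus AR(1) likelihood absorbs feedback that runs through earlier recorded troughs, as the last row of the table shows. Observation also starts with posaconazole, so the first CRP values largely precede exposure. This stands in part. The protection depends on the assumptions and on sample size: with 7-day feedback through recorded troughs the slope was 0.075 at 30 patients and 0.100 at 150. The bias is thus possible, not certain.

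A second defence is that splitting by indication does not cure the problem. This stands. In the fourth set-up the treated slope stays low (0.081, 0.062 and 0.031 at feedback 0.5, 1 and 2). With a standard error of 0.047, a prophylaxis slope of 0.10 has power Φ(0.10/0.047 - 1.96) = Φ(0.17), about 57%. Nor is the prophylaxis group entirely clean, because secondary prophylaxis may include residual infection. The split can supplement the pooled test but not replace it.

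A reader might also infer four stronger things that the documents do not support:

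- That pooling creates the bias. Step 3 shows that it dilutes it.
- That the protocol says exposure drives outcome or CRP. It speaks of an association with outcome and of described relationships, and never links the level to CRP.
- That the bias always favours the expected absence of influence. It does so only if the true effect is an increase; with no true effect it yields a false decrease, which contradicts that expectation.
- That the planned comparison with the earlier voriconazole study is biased for the same reason. It uses matched patients, the matching variables are not given, and a similar path could act for both drugs.

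**Conclusion.** The point holds as a limited one. Section 10.2 cannot tell inflammation acting on the level from low levels contributing to CRP in treated patients, and leaving out indication hides any difference between the groups. If the reverse path exists, any bias in the treated slope is downward.

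Its size is unknown. At an assumed feedback of -1 and a true slope of 0.10, the pooled slope was about 0.07 to 0.09 in most set-ups and unbiased in one. With no true effect, rejections ran from about the nominal 5% up to 26%. Only the direction, and the ordering of the groups, should be relied on. A reader might take the low end of that slope range as the expected loss, but other equally plausible autocorrelations bring it close to nothing. All of this rests on a link from level to CRP that the documents do not state. The remedy is cheap and worth making, but the point does not invalidate the planned model.

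**What to change.** In section 10.2:

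1. Add indication on the sampling day (treatment of active fungal infection versus prophylaxis) to the covariates.
2. As a sensitivity analysis next to the pooled test, fit a CRP-by-indication model and report the CRP slope with its 95% CI in each group. Do not rely on the interaction p value: it rejected in only about 14 to 24% of runs at feedback -1.
3. State in the interpretation that the slope in treated patients may still carry reverse causation.

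Do not tie the conclusion to the signs of the slopes. Suppose a rule withheld a conclusion of no influence whenever the prophylaxis slope is positive and the treated slope lower. With no true effect, no feedback and equal precision, two independent slopes meet that condition in 45°/180° = 25% of studies with a pooled slope at or below zero, and in half of those with a pooled slope near zero.

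The cost is a few lines of analysis plan and two model terms. Indication should be available from the medical chart already used for data collection (section 8.3). The group slopes are less precise, with standard errors roughly 1.4 times the pooled one if half the patients are in each group, and more in the smaller group if the split is uneven.
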